## 5.0 TREATMENT PLAN

### 5.1 Schema

Figure 1 Study Schema

LCCC 1841 is a multicenter open-label, single-arm, pilot study designed to investigate the antitumor effects of acalabrutinib in subjects with relapsed primary central nervous system (CNS) lymphoma, and relapsed secondary CNS lymphoma with no evidence of current systemic disease. Rb PET/CT will be performed at screening, at Cycle 3 Day 1 and at Cycle 7 Day 1 in the first 5 subjects at the University of North Carolina with parenchymal brain disease who consent to this testing. Subjects will continue on treatment until disease progression or discontinuation of treatment due to an adverse event. During the study, 15 evaluable subjects (per [section 8.4](#)) will be enrolled and treated. Up to 16 subjects (15 evaluable subjects) will receive acalabrutinib at the dose of 100 mg every 12 hours (**Table 1**).

Table 1 Treatment dosage and administration

REGIMEN DESCRIPTION					
Agent	Precautions	Dose	Route	Schedule	Cycle Length
Acalabrutinib	Take acalabrutinib with or without food	100mg	oral	Every 12 hours	4 weeks (28 days)

## 5.2 Toxicities and Dosing Delays/Dose Modifications

Any subject who receives at least one dose of acalabrutinib on this protocol will be evaluable for toxicity. Each subject will be assessed periodically for the development of any toxicity according to the [Time and Events table](#). Toxicity will be assessed according to the NCI Common Toxicity Criteria for Adverse Events (CTCAE), version 5.0.

If a subject experiences a toxicity or other intolerable AE suspected to be at least possibly related to acalabrutinib treatment during the course of therapy, then acalabrutinib should be withheld, as necessary, until the AE resolves or stabilizes to Grade  $\leq 1$  or baseline. Dose modifications for the following treatment-emergent toxicities are provided in **Table 2**. If/when treatment is resumed, the subject should proceed with the treatment schedule based on when the subject completed cycle 1 day 1; meaning that the schedule will not be paused when drug is held. If acalabrutinib is held for >14 consecutive days, then the subject should be permanently discontinued from study treatment and proceed to follow-up.

**Table 2. Acalabrutinib Dose Modifications**

CTCAE Grade	Acalabrutinib Dose Modifications
Hematologic Toxicities	
Neutropenia	
Grade $\leq 3$	No dose modification is required
Grade 4, initial or second occurrence	Hold acalabrutinib until recovery to Grade $\leq 1$ or baseline; may restart at original dose level 
Grade 4, third occurrence	Hold acalabrutinib until recovery to Grade $\leq 1$ or baseline; restart at one dose level lower (100 mg QD) 
Grade 4, fourth occurrence	Discontinue acalabrutinib
Thrombocytopenia	
Grade 1 or 2	No dose modification is required
Grade 4, or Grade 3 in presence of significant bleeding, initial or second occurrence	Interrupt acalabrutinib.  Once toxicity has resolved to Grade 1 or baseline level, acalabrutinib may be resumed at 100 mg approximately every 12 hours.
Grade 4, or Grade 3 in presence of significant bleeding, third occurrence	Interrupt acalabrutinib.  Once toxicity has resolved to Grade 1 or baseline level, acalabrutinib may be resumed at a reduced frequency of 100 mg once daily.
Grade 4, or Grade 3 in presence of significant bleeding, fourth occurrence	Discontinue acalabrutinib
Nonhematologic Toxicities	
Nausea, Vomiting, or Diarrhea	
Grade 1 or 2	No dose modification is required
Grade $\geq 3$ , initial or second occurrence	Interrupt acalabrutinib.

	Once toxicity has resolved to Grade 1 or baseline level, acalabrutinib may be resumed at 100 mg approximately every 12 hours
Grade $\geq 3$ , third occurrence	Interrupt acalabrutinib.  Once toxicity has resolved to Grade 1 or baseline level, acalabrutinib may be resumed at a reduced frequency of 100 mg once daily
Grade $\geq 3$ , fourth occurrence	Discontinue acalabrutinib

 Neutrophil growth factors are permitted per American Society of Clinical Oncology (ASCO) guidelines [38] and use must be recorded on the electronic case report form (eCRF).

As appropriate, certain laboratory abnormalities may warrant more frequent monitoring (e.g., once per week) until abnormalities have recovered to Grade  $\leq 1$ . If the subject tolerates a reduced dose of acalabrutinib for  $\geq 4$  weeks then the dose may be increased to the next higher dose level, at the discretion of the investigator. Such re-escalation may be particularly warranted if further evaluation reveals that the AE that led to the dose reduction was not treatment-related. The maximum dose of acalabrutinib is 100 mg BID.

Treatment with acalabrutinib should be withheld for any unmanageable, at least possibly related study drug-related toxicity that is Grade  $\geq 3$  in severity. Consider the benefit-risk of withholding acalabrutinib for 3 to 7 days pre- and post-surgery depending on the surgery and the risk of bleeding (Refer to [Section 6.1.6](#)).

### 5.3 Prohibited and Concomitant Medications

CYP3A-mediated oxidation is the major route of metabolism of acalabrutinib in humans. CYP3A4/5 is the predominant CYP isoform responsible for metabolism of acalabrutinib. Therefore, additional strong or moderate inhibitors of CYP3A4 and strong and moderate inducers of CYP3A4 are prohibited.

A frequently updated P450 drug interaction table is available at: <http://medicine.iupui.edu/clinpharm/ddis/>.

If medically justified, subjects may be enrolled if such inhibitors or inducers can be discontinued or alternative drugs that do not affect these enzymes can be substituted at least 7 days before first dose of acalabrutinib.

Acalabrutinib is not a potent direct inhibitor of CYP3A4 and is not anticipated to be a perpetrator of drug interactions at the level of systemic inhibition of CYP3A4.

#### For Subjects on Acalabrutinib Capsule Formulation

Subjects should avoid the use of calcium carbonate-containing drugs or supplements for a period of at least 2 hours before and at least 2 hours after taking acalabrutinib. Use of omeprazole, esomeprazole, lansoprazole or any other proton

pump inhibitors while taking acalabrutinib is not recommended due to a potential decrease in study drug exposure. Use of proton-pump inhibitors during the study is also prohibited. It is recommended that subjects receiving proton pump inhibitors should switch to H2-receptor antagonists or antacids prior to enrollment to this study.

Although the effect of H2-receptor antagonists (such as famotidine or ranitidine) on acalabrutinib absorption has not been evaluated, if treatment with an H2-receptor antagonist is required, the H2-receptor antagonist should be taken approximately 2 hours after an acalabrutinib dose.

### **Vaccination Guidance**

Based on nonclinical data, no changes are recommended to standard of care practices with regard to vaccinations in subjects treated with acalabrutinib. As appropriate, vaccines consistent with standard practices for specific subject populations (eg, patients with CLL) should be used.

The patient handout in [Appendix E](#) should be provided to subjects to inform them of drugs to avoid taking while they are receiving study medications.

## **5.4 Duration of Therapy**

In the absence of treatment delays due to adverse events, treatment may continue until:

- Disease progression
- Inter-current illness that prevents further administration of treatment
- Unacceptable adverse event(s)
- Pregnancy
- Subject decides to withdraw from study treatment,
- General or specific changes in the subject's condition render the subject unacceptable for further treatment in the judgment of the investigator, or
- Subject is lost to follow up

## **5.5 Duration of Follow Up**

All subjects will be followed every 3 months ( $\pm 1$  month) for survival for 5 years or until death, whichever occurs first, starting from time the subject discontinues study treatment. To document survival, subjects will either be contacted directly, or their medical record will be checked. Subjects removed from treatment prior to progression (e.g. due to adverse event(s) or withdraw from treatment) will have imaging scans (MRI) annually for 2 years or until death, whichever occurs first, from the time they discontinue study treatment.

## 5.6 Study Withdrawal

Subjects will be removed from protocol therapy and the PI notified when any of the criteria listed in section 5.4 apply. The reason for discontinuation of protocol therapy will be documented on the eCRF.

If a subject decides to withdraw from the study (and not just from protocol therapy) an effort should be made to complete and report study assessments as thoroughly as possible. At the time of withdrawal, the investigator should attempt to establish as completely as possible the reason for the study withdrawal.

- The subject should be asked if they are willing to allow for the abstraction of relevant information from their medical record in order to meet the long term follow up (e.g., survival) objectives outlined in the protocol.
- A complete final evaluation at the time of the subject's study withdrawal should be obtained. While study participants are never required to provide a reason for their decision to withdraw, the subject should be asked if they are willing to share their reason for withdrawing, and if yes, the reason should be recorded in the eCRF.
- If the subject is noncompliant and does not return for an end of study follow up assessment, this should be documented in the eCRF.
- If the reason for removal of a subject from the study is an adverse event, the principal specific event will be recorded on the eCRF.

Excessive subject withdrawals from protocol therapy or from the study can render the study un-interpretable; therefore, unnecessary withdrawal of subjects should be avoided.

## 5.7 Off-Study Criteria

Subjects will be considered off study by any of the following criteria:

- Subjects have fulfilled all study activities including follow-up activities and no further data collection is needed
- Subject withdraws consent for treatment and any further data collection
- Death
- Lost to follow-up
- Subject starts a new anti-cancer therapy
- Situations in which the treating physician feels it is in the best interest for the subject to not continue in the study

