### 1.2 Disease Background

PCNSL is an uncommon variant of extranodal non-Hodgkin lymphoma (NHL) that involves the brain, leptomeninges, eyes, or spinal cord without evidence of systemic disease. PCNSL represents approximately 4% of newly diagnosed primary CNS tumors [3, 4]. Secondary involvement of the CNS from systemic NHL may affect the nervous system at every level, including peripheral nerve, spinal nerve root, spinal cord, meninges, and brain. Such involvement may include direct invasion or compression of these structures, as well as non-invasive paraneoplastic effects of NHL. Both relapsed primary (PCNSL) and secondary CNS lymphomas (SCNSL) have a dismal prognosis, with untreated patients living for only several months [5]. Most data evaluating relapsed PCNSL are retrospective in nature, but traditional options are limited in this situation and include radiation, temozolomide, etoposide and cytarabine, all with modest response rates and poor long-term survival [5]. Furthermore, many of these patients are heavily pretreated and may have difficulty tolerating very aggressive cytotoxic chemotherapy regimens. In a study of aggressive chemotherapy in patients with SCNSL, the CR rate was only 22% with a one-year overall survival (OS) of 25% demonstrating the need for novel approaches other than traditional cytotoxic agents [6]. Therefore, more effective and well tolerated regimens are desperately needed.

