#### 3.2 Secondary Endpoints

- 3.2.1** Toxicity will be classified and graded according to the National Cancer Institute's Common Terminology Criteria for Adverse Events (CTCAE, version 5.0).
- 3.2.2** Progression-free survival (PFS) is defined from the date of initiating study treatment to the date of disease progression per the [International Primary CNS Lymphoma Collaborative Group response assessment criteria](#) [37] or death as a result of any cause.
- 3.2.3** Complete Response (CR) is defined using the [International Primary CNS Lymphoma Collaborative Group response assessment criteria](#) for primary CNS lymphoma [37].
- 3.2.4** Duration of response (DoR) is defined as time from documentation of tumor response to disease progression according to the [International Primary CNS Lymphoma Collaborative Group response assessment criteria](#) [37].
- 3.2.5** OS will be measured from the date of initiating study treatment to the date of death or 5 years (whichever is first). Subjects who have not died by the analysis data cut-off date will be censored at their last date of contact.

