18. Mini-Mental State Examination (MMSE) is performed at screening, C7D1, and then every 6 months while on the study treatment. A final MMSE will be performed at the end of treatment visit.
19. From the time subjects discontinue study treatment, they will be followed for survival every 3 months ( $\pm$ 1 month) for 5 years or until death, whichever comes first. To document survival, subjects will either be contacted directly, or their medical record will be checked.

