### 10.3 Data Analysis Plans

Analysis of efficacy will be conducted following pre-specified inference rule on rejecting the null hypothesis:  $H_0: \text{ORR} \leq 50\%$ . Specifically, we will reject the null hypothesis if and only if there are  $>9$  ORs in the 15 subjects. The main analysis is inferential because we frame it as a hypothesis-testing problem. We will also calculate 2-sided 95% clopper-Pearson confidence interval for ORR.

Secondary endpoints include PFS, CR, DoR, overall survival, and safety/toxicity. Analyses of secondary endpoints will be descriptive. Specifically, time-to-event outcomes like PFS, DoR, and OS will be analyzed using Kaplan-Meier method, and Kaplan-Meier survival curves will be provided. Categorical outcomes like CR, and safety/toxicity (different types of AEs) will be summarized using frequencies.

- For the primary outcome, ORR, there should be no missing data. We will replace non-evaluable cases with new subjects so that the total sample size of 15 evaluable subjects is guaranteed.
- There is only one test for the primary endpoint and hence there is no multiplicity issue.

Per exploratory endpoints:

[REDACTED]

[REDACTED]

[REDACTED]

[REDACTED]

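### Section 5.7 takes a subject off study at the start of a new anti-cancer therapy, contradicting the 5-year survival follow-up and, if applied literally, censoring OS informatively

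*Combined protocol and SAP*

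**What the plan says.** **Off study.** Section 5.7 opens with "Subjects will be considered off study by any of the following criteria", so one criterion is enough. One of them is "Subject starts a new anti-cancer therapy". The others include death, loss to follow-up, withdrawal of consent to treatment and further data collection, and completion of all activities including follow-up.

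**Survival follow-up.** Section 5.5 follows all subjects every 3 months "for survival for 5 years or until death, whichever occurs first, starting from time the subject discontinues study treatment", by direct contact or a check of the medical record. Footnote 19 repeats the period: "for 5 years or until death, whichever comes first". Neither names new therapy as an end.

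**OS analysis.** Section 3.2.5: "Subjects who have not died by the analysis data cut-off date will be censored at their last date of contact". Section 10.3: "time-to-event outcomes like PFS, DoR, and OS will be analyzed using Kaplan-Meier method". New therapy is not mentioned in either place, and no sensitivity analysis is given.

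**Imaging after stopping before progression.** Under section 5.5 these subjects "will have imaging scans (MRI) annually for 2 years or until death". Footnote 9 gives the same frequency and duration but ends the scans at disease progression.

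**The concern.** OS is a stated secondary objective (2.2.5). Kaplan-Meier is valid when subjects censored at a given time have the same later risk of death as those still followed. New therapy mostly follows progression, and section 1.2 describes relapsed CNS lymphoma as a disease "with untreated patients living for only several months". Losing subjects at that moment removes them just as their risk of death changes, so the censoring is informative. In a multicenter study, one site could follow 5.5 and another 5.7, and the completeness of OS would then depend on the site.

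The clause has a safety side too. Section 9.3.1 keeps drug-related serious events reportable while a subject is on study. Read literally, 5.7 ends that at new therapy.

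The secondary point concerns PFS and DoR. A subject who stops for an adverse event or by choice moves to annual scheduled MRI, so progression may be dated late. A dose hold of more than 14 consecutive days (5.2) is one protocol route to this group.

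**Working it through.** **1. Can the passages be read together?** Reading off study as off treatment would remove the conflict, but stopping treatment has its own list in 5.4. The remaining 5.7 criteria describe the end of data collection. Section 5.6 seeks survival data from the record even when a subject withdraws from the study; 5.7 makes no such provision for a subject who only starts another drug. Sections 9.2 and 9.3.1 already use new anticancer therapy as an end to routine AE and SAE collection, which is a natural home for the clause. The conflict stands.

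**2. Stated figures.** The documents give no OS, PFS or DoR figure to reproduce. The only design figures concern ORR: with 15 evaluable subjects and rejection at 10 or more responders, the exact binomial gives power 0.7216 (stated 72%) and one-sided type 1 error 0.1509 (stated 0.15). Survival follow-up does not enter them.

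**3. Possible effect on OS.** None of these inputs is in the documents; all are assumptions:
- median PFS 3, 4 or 6 months, exponential, with 15% of PFS events being deaths
- median post-progression survival 4 or 8 months, exponential
- 30%, 50% or 70% of progressors start new therapy 1 to 4 weeks after progression, independently of prognosis, and are then lost

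Kaplan-Meier results from 400,000 simulated subjects per scenario (selected rows):

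| Median PFS | Post-progression median | Re-treated | Median OS, followed | Median OS, off study | 12-month OS, followed / off study | Deaths seen of 15 |
|---|---|---|---|---|---|---|
| 3 | 8 | 30% | 10.9 | 11.3 | 0.46 / 0.48 | 11.3 |
| 4 | 4 | 50% | 8.8 | 10.3 | 0.35 / 0.43 | 9.3 |
| 6 | 4 | 70% | 11.1 | 15.6 | 0.46 / 0.61 | 7.0 |
| 6 | 8 | 70% | 15.1 | 19.5 | 0.60 / 0.70 | 6.5 |

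Over all 18 scenarios the median is overstated by 0.4 (11.3 − 10.9) to 4.5 (15.6 − 11.1) months, and 12-month OS by 2 to 15 points. Deaths seen are 43% to 77% of subjects, or 6.5 to 11.6 of 15.

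Check on the count: at 70% re-treatment the share lost cannot exceed 0.85 × 0.70 = 0.595, so at least 15 × (1 − 0.595) = 6.1 deaths are seen. The simulation gives 6.5 to 7.0 because some subjects die before new therapy starts.

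**4. Scan delay.** On treatment, footnote 9 gives MRI at C3, C5, C7, C10, C13, C19 and C25 Day 1. With 28-day cycles these are weeks 8, 16, 24, 36, 48, 72 and 96: 8-weekly to week 24, 12-weekly to week 48, 24-weekly to week 96, then annual. For exponential progression at rate λ = ln 2 / median and scan interval I, the mean lag is I / (1 − exp(−λI)) − 1/λ.

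- Annual, median 4 months: 12 / 0.875 − 5.77 = 7.9 months.
- Annual, median 6 months: 12 / 0.75 − 8.66 = 7.3 months.
- At the same medians: about 1.0 month for 8-weekly, 1.5 for 12-weekly and 3.1 for 24-weekly scans.

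The annual figures are upper bounds, because they allow neither death nor a symptom-driven scan to end the wait. Death is a PFS event (3.2.2). With an assumed exponential median of 3 to 6 months from progression to death, the mean lag falls to about 3 to 5 months. If symptoms also prompt a scan at an assumed median of 1 to 2 months, it falls to about 1 to 2 months. The cap at death applies to PFS only, since the DoR definition in 3.2.4 does not list death.

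**The case against.** The strongest reply is that the OS bias may never arise. Section 5.5 says all subjects are followed, footnote 19 repeats it, the medical record is an accepted source, and 3.2.5 does not name new therapy as a censoring event. A site that follows 5.5 loses nothing. This stands: the bias is conditional on 5.7 being applied. It does not remove the contradiction or the chance that sites differ.

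Three stronger readings are tempting, and the documents do not support them.

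- A reader might infer that, if 50% to 70% of progressors are re-treated, 50% to 70% of OS times end near progression and only 5 to 7 of 15 subjects inform later survival. That needs every subject to reach progression alive and to be lost. In the simulation the same re-treatment rates leave 6.5 to 9.3 observed deaths.
- A reader might infer that OS is certainly overstated. The simulation is upward throughout because re-treatment was made independent of prognosis. If fitter subjects are re-treated, those left under observation do worse, which pulls the other way.
- A reader might infer that leaving treatment changes the delay in seeing progression from about 1 month to 7 or 8. The 1-month comparator holds only to week 24, and after week 96 both schedules are annual. The larger figure ignores death and symptom-driven scans. Footnote 9 provides for scans on signs or symptoms, although in its on-treatment sentence.

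It is also fair to say that annual MRI is a choice on which 5.5 and footnote 9 agree. Only the end of those scans differs between them.

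**Conclusion.** The contradiction between section 5.7 and section 5.5 with footnote 19 is explicit and should be corrected. Where 5.7 is applied literally, OS is censored informatively near progression. Under the stated assumptions the median shifts by about 0.4 to 4.5 months upward; these months are illustrations, and with fitness selection neither size nor direction is certain.

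The secondary point is smaller. It concerns only subjects who stop before progression, a number the documents do not allow one to estimate, and it bears on PFS and DoR. The 7 to 8 month lag is an upper bound.

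OS, PFS and DoR are secondary and descriptive, and the 2-month ORR test is untouched. The correction is still worth making, because survival data that were not collected may be hard to recover and this pilot is meant to inform a larger study.

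**What to change.** 1. Delete the new-therapy bullet from section 5.7, or limit it to the end of adverse event collection in line with 9.2 and 9.3.1. If it is limited, keep the 9.3.1 reporting of drug-related serious events clear of it.
2. State in 5.5 and footnote 19 that survival follow-up continues after any new anti-cancer therapy, and record the start date of that therapy at the existing 3-monthly contact or record check.
3. For subjects who stopped before progression, abstract the progression date from standard-of-care imaging at the same checks, for PFS and DoR. State how PFS and DoR treat new therapy begun before progression. Standard-of-care scans are irregular, so report the scan dates too.
4. Reconcile section 5.5 and footnote 9 on whether the post-treatment scans end at death or at progression.

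The cost is protocol wording and a few eCRF fields (new-therapy start date, progression date, scan date). No visit, scan or treatment rule is added.

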## 6.0 DRUG INFORMATION

### 6.1 Acalabrutinib (CALQUENCE)

**Brief Description:** Acalabrutinib (also known as ACP-196 and/or Calquence®) is a selective, irreversible small molecule inhibitor of BTK.. Calquence® has been approved in the United States and other markets for the treatment of adult patients with mantle cell lymphoma (MCL) who have received at least one prior therapy, chronic lymphocytic leukemia (CLL), and small lymphocytic lymphoma (SLL).

**Supplier:** AstraZeneca Pharmaceuticals LP, 2017; Wilmington, DE. A commercial supply of acalabrutinib will be supplied by AstraZeneca at no cost to the subject.

**Active ingredient:** acalabrutinib

